2. To compare the findings with a previously completed study using a population of adults with typical (i.e., normal) reading abilities (Cummene et al., in press).
3. To better understand how the speech production system contributes to reading performance. The information will help refine the currently accepted speech and reading neural models.

Study Design | Trial Design

Participant | Subject Criteria

Inclusion criteria. Thirty adults (i.e., ≥ 18 years of age) of either sex or identified gender with diagnosed or self-reported dyslexia will be recruited to participate in a within subjects repeated measures design. Thirty participants (18+) without dyslexia will also be recruited as a control

group. All participants will need to be proficient in English as the assessment materials are only available in English.

Reading disorders are rarely formally diagnosed because of many factors including but not limited to: timing in educational system for assessments, comorbidities with higher priority disorders (i.e., apraxia of speech, ADHD, etc.) and cost. Self-reported reading challenges are more accurate at identifying potential participants. Self-reported reading disorders will be confirmed/verified prior to enrollment via standardized reading measures.

Exclusion criteria. Participants must have no personal or family history of adverse reactions to anesthetics to complete all the conditions. Participant who cannot consume sugary products will be excluded. Additional exclusion criteria include: severe kidney disease; severe liver disease; treatment with class I antiarrhythmic drugs (such as mexiletine) or class III antiarrhythmic drugs (such as amiodarone); lack of integrity of oral mucosa; allergy to non-medicinal ingredients and preservatives (and related compounds) of Lidocaine Viscous, such as methylparaben, propylparaben, paraaminobenzoic acid, saccharin, artificial colours and flavour; concomitant use of another anaesthetic containing lidocaine or another amide; participant being pregnant or suspecting that she might be pregnant; negative pregnancy test is required for women of childbearing potential.

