3. Any participant reporting a personal or family history of adverse reactions to anesthetics will not be enrolled. If a participant reports any concerns or adverse reactions during the collection session, collection will immediately stop, and their participation discontinued.
4. If the participant is enrolled, they will be assigned a randomly generated identification number. All of their files and documents will be labelled with this number.
5. Each participant will also be randomly assigned to one of six possible task orders. Neither participants nor experimenters will be blinded to these conditions. This is documented in a hard-copy log.
6. Participants will be fit with an fNIRS cap to measure brain signals.
7. Then complete three computer generated tasks under four conditions (a, b and c will be randomized):
 - a. No sensory perturbation
 - b. Lollipop
 - c. Bite bar
 - d. Lidocaine – this condition will always be completed last.

8. The comparators to the lidocaine are no sensory perturbation, a candy lollipop and candy bite bar. All candy is obtained from the grocery store and are individually packaged. The lidocaine will be dispensed by a pharmacist and administered by the research team.
9. For the three computer generated tasks (randomly administered), accuracy and response time will be measured by the computer:
 - a. Task 1 (orthographic lexical decision): involves deciding whether a series of letters formulates a word or a nonword. Individuals will press the 'g' key if it is a word and the 'h' key if it is a nonword. Stimuli are single, monosyllabic, 4-7 letter length, words and nonwords.
 - b. Task 2 (phonological lexical decision): involves deciding whether a series of letters sounds out a word or a nonword. Individuals will press the 'g' key if it is a word and the 'h' key if it is a nonword. Stimuli are single, monosyllabic, 4-7 letter length, words and nonwords.
 - c. Task 3 (picture categorization): requires participants to make a judgement about whether a visually presented object is an animal or not. They will press 'g' if the object is an animal, and 'h' if it is not an animal.
10. Complete a short questionnaire rating and describing the numbness caused by the lidocaine (less than 5 minutes to complete).

Treatment

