The lidocaine condition will always be lastly completed so its effects will not interfere with the other conditions. Each participant will be asked to complete a questionnaire after collection to localize and rank their numbness on a provided schematic. And adverse events reported by the participant will be recorded on this document and reported immediately to the qualified investigator. After the collection session is over, the participant will be instructed to report to their nearest emergency room if they experience any reactions or adverse effects. Topical anesthetics in the mouth may impair swallowing. The numbness may also increase the risk of unintentional biting (e.g., cheek). The qualified investigator, an otolaryngology head and neck surgeon, will follow-up with the subject as she deems appropriate. All serious unexpected adverse drug reactions (SUSARs) will be reported to Health Canada as mandated per C.05.014 (1) of the FDR.

Budget Considerations

Participants will be offered a small honorarium (\$20.00) for taking part in the study.

Experiment Location

6-104, Clinical Sciences Building, University of Alberta.

Statistical Analysis

Given the between groups nature of the sensorimotor perturbation (i.e., lidocaine vs. no lidocaine groups), we will first run a $2 \times 2 \times 4 \times 2$ ANOVA with group (lidocaine vs. no lidocaine), task (spell vs. sound), word type (exception words, regular words, pseudohomophones, nonwords), and time (pre-lidocaine vs. post-lidocaine), as the factors of interest. If the 4-way interaction is significant, a series of mixed ANOVAs will be run to test the effect of sensorimotor perturbation for each of the reading tasks. The independent variables will be time (pre-perturbation vs. post-perturbation), word type (exception, regular, pseudohomophone, nonword) and group. An ANOVA was also be run to test the effect of the sensorimotor perturbation for the control picture categorization task, with the independent variables including time (pre-perturbation vs. post-perturbation) and group. The dependent variable will include response time and accuracy. Bonferroni corrected t -tests were used to explore significant effects of the lidocaine on task performance. No interim analyses are planned. The data will be analyzed when thirty subjects have participated.

Data | Documents

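### The trial randomises order but no planned model contains order, position or session, and no blocking of orders within reader group is stated, so practice or fatigue drift stays in the error term

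*Combined protocol and SAP*

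**What the plan says.** Methodology step 5 states: "Each participant will also be randomly assigned to one of six possible task orders". Step 7 describes "three computer generated tasks under four conditions (a, b and c will be randomized", with the fourth condition, lidocaine, fixed: "this condition will always be completed last". Step 9 randomises something else as well: "For the three computer generated tasks (randomly administered), accuracy and response time will be measured by the computer". Three conditions can be ordered in six ways, and so can three tasks. The sentence after the one in step 5 refers to conditions, which leans towards the first meaning without settling it.

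Two reader groups are planned under the subject criteria: "Thirty adults (i.e., ≥ 18 years of age) of either sex or identified gender with diagnosed or self-reported dyslexia will be recruited", and "Thirty participants (18+) without dyslexia will also be recruited as a control" group. The text describes no list method, block size or stratification factor for the orders.

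The Methodology section also sends 20% of participants (12 people) through the protocol in two sessions, to look at order and fatigue. It does not say how the 12 are chosen, how the conditions are divided between sessions, or how their data are analysed.

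The first ANOVA in the Statistical Analysis section has group (lidocaine or none), task, word type and time. For the follow-up models, "The independent variables will be time (pre-perturbation vs. post-perturbation), word type (exception, regular, pseudohomophone, nonword) and group". The picture task has time and group. None has a term for order, position or session.

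**The concern.** One session of up to 90 minutes repeats three timed tasks under four conditions, and response time is part of the primary endpoint. Responses may quicken with practice or slow with fatigue. The plan recognises this: it randomises order and sets aside a two-session subset. It then leaves order out of every model.

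Randomising order protects the contrasts among no perturbation, lollipop and bite bar from systematic order bias. It does not remove the scatter that order causes. A participant who had the lollipop first and the bite bar third carries two positions of drift in that difference, and another participant carries the opposite. Unless position is fitted, this spread counts as error. The first objective covers all three perturbations, so these contrasts are study aims, and with 30 people per reader group the precision is worth recovering.

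**Working it through.** **The plan's own figures.** Orders of the three randomised conditions: 3! = 6, which matches step 5. Orders of the three tasks: also 3! = 6. If both were randomised independently there would be 6 × 6 = 36 combinations. The two-session subset is 0.20 × 60 = 12, as stated.

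**Position moments (conditions a–c in positions 1–3, lidocaine in 4).** Over the six orders:
- A given condition sits at 1, 1, 2, 2, 3, 3. The mean is 2 and the variance is (1+1+0+0+1+1)/6 = 2/3.
- The gap between two of the three conditions is ±1 in four orders and ±2 in two. Its mean is 0 and its mean square is (4×1 + 2×4)/6 = 2.
- Lidocaine minus no perturbation has a mean lag of 4 − 2 = 2 positions, with variance 2/3.

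**Variance added.** Assume drift of p ms per position. It adds 2p² to the per-person variance of a contrast among a–c, and (2/3)p² to lidocaine versus no perturbation. With SD the contrast SD excluding order and V the added variance, the information lost is V/(SD² + V), and the standard error is multiplied by √(1 + V/SD²). Both p and SD are assumptions; the documents give neither.

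| p (ms) | SD (ms) | a–c: V | a–c: information lost | a–c: SE increase | lidocaine vs none: V | lidocaine vs none: information lost | lidocaine vs none: SE increase |
|---|---|---|---|---|---|---|---|
| 20 | 100 | 800 | 7.4% | 3.9% | 267 | 2.6% | 1.3% |
| 20 | 60 | 800 | 18.2% | 10.6% | 267 | 6.9% | 3.6% |
| 30 | 100 | 1800 | 15.3% | 8.6% | 600 | 5.7% | 3.0% |
| 30 | 60 | 1800 | 33.3% | 22.5% | 600 | 14.3% | 8.0% |

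**In power terms.** Take a paired test with n = 30, two-sided 0.05 (assumed) and 80% power when position is fitted. Power without the term is Φ(2.80/√(1 + k(p/SD)²) − 1.96), with k = 2 for a–c and k = 2/3 for lidocaine versus none.
- p/SD = 0.2: 76.9% among a–c, 79.0% for lidocaine versus none.
- p/SD = 0.3: 73.2% and 77.7%.
- p/SD = 0.5: 62.8% and 73.7%.

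**Allocation.** The method is not stated. If it were simple randomisation of 30 people to six orders, the chance of exactly 5 per order would be 30!/(5!⁶ × 6³⁰) = 0.04%. The chance that some order receives 2 or fewer would be about 53% (200,000 simulated draws). Permuted blocks of six give 30/6 = 5 per order in each reader group.

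**Why blocking and the model term are both needed.** With exact balance the position gaps sum to zero, so common linear drift drops out of the estimated mean contrast. It stays in the spread of the individual differences, and hence in the ANOVA error, unless position is fitted.

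**What neither step reaches.** Lidocaine versus no perturbation carries a mean shift of 2p, or 40–60 ms at the assumed p, because lidocaine is never in another position.

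**The case against.** The strongest reply has four parts.

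- **Order is already handled.** Conditions a–c are randomised, which protects against systematic order bias, and the two-session subset shows that order and fatigue were considered. This stands as far as it goes. What is missing is any analysis of the subset and any order term in the models.
- **The contrasts at issue are not in the written analysis.** Its group factor is lidocaine or no lidocaine, although every participant receives lidocaine. No reader-group factor and no separate lollipop or bite-bar factor appears. This also stands: the contrasts come from the first objective and the two-group recruitment, so a position term has a place only once the model is reconciled with the design.
- **Orders need not be unbalanced.** A reader might infer that they are unbalanced between dyslexia and control. The documents do not support that. A blocked list is also random assignment, and only the absence of a stated method can be asserted. The 53% and 0.04% figures hold only under simple randomisation.
- **Chance imbalance is not an extra bias.** A reader might count the chance gap between reader groups as bias on top of the lost precision. Under simple randomisation that gap has SD √(4/30) = 0.37 positions, about 7 ms at p = 20. This equals √(2 × 2p²/30) = 7.3 ms, the same 2p² seen at group level. It is sampling error already counted.

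**Conclusion.** The point holds as one of efficiency and specification. The plan randomises order and names it as a concern, but no model contains order, position or session, and no blocking within reader group is stated. For contrasts among no perturbation, lollipop and bite bar, the loss is 7–33% of the information, or a 4–22% larger standard error. For lidocaine versus no perturbation it is about 3–14%, or 1–8% on the standard error.

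These sizes rest on assumed linear drift of 20–30 ms per position, common to all participants, and an assumed contrast SD of 60–100 ms. At the lower end the loss is small. A position term removes shared drift only; differences between people in how they drift would remain.

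A reader might also infer that modelling order would clear the lidocaine comparison of practice or fatigue. It would not. Lidocaine is always fourth, so its position effect cannot be estimated, and extending a slope from positions 1–3 would rest wholly on the linearity assumption.

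**What to change.** 1. State whether the six orders are orders of conditions a–c or of the three tasks, and how the other sequence is generated.
2. Allocate the orders in permuted blocks of six, separately for dyslexia and control, giving 5 per order per group. Say which order a replacement for a withdrawn participant receives, so that the balance is kept.
3. Reconcile the model with the design: condition as a within-person factor and reader group as the between-person factor, with task and word type as planned. Add position (1–3, for conditions a–c only), position by reader group, and session for the two-session participants. Say how those 12 are selected and how their conditions are divided between sessions.
4. State that the position term adjusts the a–c conditions only, and that lidocaine remains confounded with last position whatever the blocking or modelling.

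The cost is one blocked list and about five degrees of freedom: two for position, two for its interaction with reader group, and one for session. The blocking has to be in place before enrolment. The model terms need only be fixed before the data are analysed, so they remain available if recruitment has already begun.

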Each participant will swish 15 mL (one tablespoon) of the Viscous Lidodan 2% in their mouth for 60 seconds, then spit into a sink. This amount is the recommended manufacturer dosage. This will occur once during the one collection session. Viscous Lidodan 2% (i.e., Lidocaine Hydrochloride Oral Topical Solution 2% USP) is a topical anesthetic. The numbing effects of Viscous Lidodan 2% should take effect after five minutes and last around 30 minutes.

No other topical oral anesthetics are permitted to have been administered in the day before the trial. No details are required on any other medications.

Safety Assessment

Safety Assessment/Monitoring and Risk Mitigation. Each participant completes a pre-collection questionnaire where it asks all subjects to report any personal or family history of adverse reactions to anesthetics. This is a hard-copy questionnaire that is completed by the participant after the informed consent form, but before collection begins. It is reviewed together with the experimenter and participant before collection commences. Participants will be informed prior to beginning the experiment that they may withdraw at any time. They will be monitored throughout the experiment by research staff for signs of distress or adverse reactions (e.g., redness, itching or swelling of skin, hives, burning, stinging, or any other skin problems, swelling of the neck area, or any difficulty with breathing). The QI will be available via phone/pager during administration of Lidocaine in case of adverse event(s) for assessment/ triage/treatment/follow-up as clinically indicated.

If any reactions or adverse effects (i.e., redness, itching or swelling of skin, hives, burning, stinging, or any other skin problems, swelling of the neck area, or any difficulty with breathing)

are observed by the experimenters during collection, the QI will be called and the experimenter will escort the participant to the hospital emergency room connected to the Clinical Sciences Building. After the collection session is over, the participant will be instructed to report to their nearest emergency room if they experience any reactions or adverse effects. Participants will be informed that they should avoid eating and drinking and exposure to extreme hot or cold temperatures (e.g. food, drink) until complete sensation has returned. The numbness may also increase the risk of unintentional biting (e.g., cheek).

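### The planned ANOVA needs a no-lidocaine group that no written procedure creates; with the groups the trial does have, the pre/post-lidocaine factor coincides with block position and no position adjustment is planned

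*Combined protocol and SAP*

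**What the plan says.** All places are in the combined protocol and SAP.

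- **Analysis (Statistical Analysis).** The model is introduced with "Given the between groups nature of the sensorimotor perturbation (i.e., lidocaine vs. no lidocaine groups". Its other factors are "task (spell vs. sound", four word types and "time (pre-lidocaine vs. post-lidocaine". The next step is conditional: "If the 4-way interaction is significant, a series of mixed ANOVAs will be run". A separate, ungated ANOVA is planned "for the control picture categorization task, with the independent variables including time (pre-perturbation vs. post-perturbation) and group". Data are to be analysed once thirty subjects have taken part.
- **Who receives lidocaine (Treatment).** "Each participant will swish 15 mL (one tablespoon) of the Viscous Lidodan 2" per cent solution. No exception is stated.
- **Order (Methodology, step 7; Safety Assessment).** The no-perturbation, lollipop and bite-bar conditions are randomised. For lidocaine, "this condition will always be completed last". The reason given is carry-over: "The lidocaine condition will always be lastly completed so its effects will not interfere with the other conditions".
- **Comparators and groups (Methodology, steps 3 and 8; Participant | Subject Criteria).** Lidocaine is compared with the other three conditions. Thirty adults with dyslexia enter a within-subjects design, and thirty adults without dyslexia serve as controls. People with a personal or family history of anaesthetic reactions are not enrolled.
- **Order and fatigue (Methodology).** Twelve participants are split over two sessions to look at these effects. No analysis of them is described.

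**The concern.** The group factor in the ANOVA does not match the trial described elsewhere in the document. The controls are defined by absence of dyslexia, not by absence of lidocaine, and people who might have had to avoid lidocaine are not enrolled. The gate on which the reading-task follow-up depends therefore has no data for one of its two group levels.

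Reading group as dyslexia versus control makes the model computable but leaves a second problem. Everyone does the lidocaine block fourth, so post-lidocaine also means fourth run of the tasks. Objective 1 asks for the effect of each perturbation in adults with dyslexia, and the primary endpoint is performance with and without perturbation. A group-by-time term removes only drift common to both groups and does not isolate lidocaine within the dyslexia group. Practice would be expected to shorten response times, the direction of the lidocaine effect the protocol reports from earlier work on the phonological task; fatigue would act the other way. The documents give neither the direction nor the size of any drift.

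**Working it through.** **1. The plan's own counts.** Three randomised conditions give 3! = 6 orders, matching the six in Methodology, step 5. (That step speaks of task orders; three tasks also give 6, and lidocaine is last either way.) Recruitment is 30 + 30 = 60, and 20% × 60 = 12 matches the two-session subset.

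**2. The ANOVA as written.** The cells number 2 × 2 × 4 × 2 = 32, half of them in the no-lidocaine group. With 60 treated and 0 untreated, 16 cells are empty. The cell-means matrix has rank 16 of 32, and the group-by-time matrix has rank 2 of 4. The four-way interaction is not estimable.

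**3. Group read as dyslexia versus control: can lidocaine be separated from position?** Take one group of n = 30, the six orders balanced, participant and condition effects, and lidocaine in block 4.

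| Position term | Columns | Rank | Lidocaine vs none estimable |
|---|---|---|---|
| Categorical | 30 + 3 + 3 = 36 | 35 | No |
| Linear | 30 + 3 + 1 = 34 | 34 | Yes, by extrapolating from positions 1–3 |

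Lollipop versus none is estimable in both models. The plan includes neither position term.

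**4. Bias of the unadjusted contrast.** With balanced orders, the no-perturbation block has mean position (1 + 2 + 3)/3 = 2 and lidocaine is at 4. A linear drift of d per block shifts lidocaine minus none by (4 − 2) × d = 2d, so 5 or 10 ms per block gives 10 or 20 ms.

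**5. Where drift reaches a planned test.** Drift and SD are assumptions, as is the 5% level, because the documents give none of them.

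*Reading tasks* (dyslexia versus control, 30 per group, independent cells, SD 60 ms, common 20 ms drift, 40,000 simulated runs): the four-way gate rejects 5.1%, against 5.0% without drift. A follow-up time effect taken alone rejects 94.8%, or 74% if drift also varies between people with SD 40 ms. Gate and time effect together reject 4.8% of all runs, or 3.7% with that variation.

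*Picture ANOVA* (ungated, no true lidocaine effect): the time effect has noncentrality N × drift² / SD² on F(1, N − 2), where SD is that of the pre/post difference. For N = 60, drift 20 ms and SD 60 ms this is 60 × 400 / 3600 = 6.67.

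| N | Drift | SD 60 | SD 85 | SD 100 |
|---|---|---|---|---|
| 60 | 10 ms | 24.6% | 14.6% | 11.9% |
| 60 | 20 ms | 71.9% | 43.5% | 33.2% |
| 30 | 10 ms | 14.3% | 9.5% | 8.3% |
| 30 | 20 ms | 42.2% | 23.8% | 18.5% |

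The N = 30 rows take the thirty in Statistical Analysis as the total analysed.

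**6. Precision of adjusted contrasts** (n = 30, independent cells, SD 60 ms).
- Unadjusted: 60 × √(2/30) = 15.5 ms.
- Linear position: the slope from positions 1–3 has SE 60/√(2 × 30) = 7.75 ms per block, so the SE is √(15.5² + (2 × 7.75)²) = 21.9 ms.
- Lexical minus picture: 60 × √(4/30) = 21.9 ms at zero correlation. Its ratio to the unadjusted SE is √(2(1 − ρ)): 1.41, 1.22 and 1.00 at ρ = 0, 0.25 and 0.5.

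**The case against.** Putting lidocaine last has a stated carry-over reason, which is not disputed here. Several safeguards also stand:

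- Common drift does not inflate the four-way gate.
- The spell-versus-sound by time term cancels drift shared by the two lexical tasks, though it also cancels any lidocaine effect shared by them.
- Comparisons among blocks 1–3 are unaffected.
- A time effect in the picture task would itself warn of drift.
- The protocol reports that lidocaine earlier speeded the phonological task but not the orthographic or picture tasks, which is not what general practice alone would suggest. That is reassuring but not decisive: the earlier study's block order is not given, and the protocol says it is unknown whether the effects hold in adults with reading disorders.

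A reader might infer that no analysis could ever recover a lidocaine effect. The documents do not support that: separation fails for an unrestricted position effect, not for a linear one. A reader might also infer that the reading-task analysis has a grossly inflated false-positive rate. Under the dyslexia-versus-control reading with common drift, the gated sequence stays near or below nominal. High rates apply to ungated tests, or to a follow-up time effect once the gate is open.

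What remains is that the gate as written cannot be computed, and that no planned analysis separates lidocaine from position within a task in adults with dyslexia.

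**Conclusion.** The point holds in two parts. The first needs no assumption beyond the written text: the group factor contradicts Treatment, Methodology and Participant | Subject Criteria; half the cells are empty; and the pre block is undefined. Figure 1 could alter this only if it showed an untreated group, and its caption describes a repeated measures design.

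The second part applies once group is read as dyslexia versus control. An unadjusted lidocaine-versus-none change then cannot be attributed to lidocaine rather than to practice or fatigue. Its size is unknown; the picture-task rates above only illustrate it under assumed drift and SD. It would be wrong to conclude that the order of administration is itself an error. The gap is in the analysis, which neither matches the design nor deals with the position effect the order creates. This should be fixed before analysis.

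**What to change.** Take the administration order as given.

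1. Reconcile the group factor in Statistical Analysis with Treatment, Methodology and Participant | Subject Criteria. Restate the ANOVA with dyslexia status between persons and the four actual conditions within person. Name the pre block. Reconcile the thirty subjects at analysis with the 60 to be recruited.
2. State that an unadjusted pre/post or lidocaine-versus-none difference, including the picture-task time effect, will not by itself be claimed as a lidocaine effect.
3. Beside the unadjusted contrast, report one or both of these sensitivity analyses for response time and accuracy: lidocaine versus none adjusted for linear block position (assumes linear drift that continues to block 4); and that difference in each lexical task minus the same difference in the picture task (assumes equal drift across tasks and no lidocaine effect on picture responses).

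Items 1 and 2 are wording. Item 3 needs no new data but costs precision: with independent cells each SE is about 1.41 times the unadjusted one (21.9 versus 15.5 ms at n = 30, SD 60 ms), less for the picture contrast if the tasks correlate positively. Neither removes the confounding without its assumptions. For example, if picture drift is half of a 20 ms lexical drift, 10 ms of bias remains.

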Women of childbearing potential (WOCBP), i.e. assigned at birth females who experienced menarche and are not sterile or postmenopausal, may be included in the study, provided that they use an acceptable method of contraception, such as: hormonal contraceptives (e.g. combined oral contraceptives, patch, vaginal ring, injectables, and implants); intrauterine device (IUD) or intrauterine system (IUS); (partner's) vasectomy, tubal ligation; double barrier methods of contraception (e.g. male condom plus spermicide, cervical cap plus spermicide, diaphragm plus spermicide). Abstinence is acceptable provided that it is consistent with the participant's usual lifestyle.

Adult participants must weigh at least 50 kg or 110 lbs to avoid any possible toxic effects from the lidocaine.

Qualified Investigator (QI) Physician:

[name], MD

[name]

[name]

[name]

Edmonton, AB

[contact]

[contact]

Subjects that do not meet these criteria when contacting researchers will not be scheduled for collection. Participants will be immediately withdrawn (i.e., collection stopped) if they are unable to perform reading assessments, they report any adverse reaction or a desire to discontinue. If the participant withdraws or their participation discontinued, their data will be retained for analysis, unless the participant requests the data be destroyed. Any withdrawn participants will be replaced with additional recruitment. No follow-up is planned for withdrawn

participants unless they experience an adverse reaction that require medical follow-up and reporting.

[figure not shown]

Figure 1. Schematic of repeated measures design

Methodology

The primary endpoint is reading response time and accuracy for each word type with and without oral perturbation.

The individual will be required to attend one collection session at the Clinical Sciences Building at the University of Alberta which will last no more than 90-minutes. Twenty percent (i.e., 12) of recruited participants will complete the the protocol below over two separate 60-minute sessions to investigate the effects of order, fatigue, etc.

During the session, participants will:

1. Read and complete an information and consent form (less than 10 minutes to complete).
2. Complete a pre-collection questionnaire to gather information such as age, sex and allergies (less than 5 minutes to complete).

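### Accuracy scored word type by word type mixes discrimination with willingness to answer 'word'; prespecify d' and criterion alongside it

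*Combined protocol and SAP*

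**What the plan says.** The Methodology section states: "The primary endpoint is reading response time and accuracy for each word type with and without oral perturbation". Step 9 adds that "accuracy and response time will be measured by the computer". For both reading tasks the response rule is "Individuals will press the 'g' key if it is a word and the 'h' key if it is a nonword". Task 1 is judged on spelling. Task 2 is judged on sound: it "involves deciding whether a series of letters sounds out a word or a nonword". The picture task uses the same two keys: "They will press 'g' if the object is an animal, and 'h' if it is not an animal".

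The Statistical Analysis section enters task, group, time and word type into an ANOVA, with the last factor given as "word type (exception words, regular words, pseudohomophones, nonwords". On outcomes it says "The dependent variable will include response time and accuracy". Bonferroni-corrected t-tests are then "used to explore significant effects of the lidocaine on task performance".

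No sensitivity index, criterion or other bias-adjusted score is defined, and no alternative key mapping is described. Accuracy is not defined further, so percent correct is the ordinary reading.

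**The concern.** A lexical decision depends on two things: how well the reader tells words from nonwords, and how readily the reader says 'word' when unsure. Percent correct for one word type cannot tell them apart, because every item of that type has the same correct answer within a task. For words it is a hit rate; for nonwords it is a correct-rejection rate.

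A participant who becomes readier to answer 'word' in one condition therefore gains accuracy on words and loses it on nonwords while reading no better or worse. In the planned ANOVA this is a word type by time effect. If pseudohomophones count as nonwords in Task 1 and as words in Task 2, as the task wording implies, it is also a task by word type by time effect. The plan would take either pattern as evidence that a perturbation acts on reading, and the third objective would carry that into models of speech and reading.

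**Working it through.** The plan gives no expected accuracy, effect size, alpha, power or item count, so it has no figure to reproduce. The check asks how large a false effect a pure change in response bias would produce.

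**Correct answers by type.** Inferred from the task descriptions; the documents give no key by type.

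| Word type | Task 1 (spelling) | Task 2 (sound) |
|---|---|---|
| Exception | word | word |
| Regular | word | word |
| Pseudohomophone | nonword | word |
| Nonword | nonword | nonword |

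**Model (assumed).** Equal-variance signal detection with criterion c:
- accuracy on items whose answer is 'word' = Φ(d'/2 − c)
- accuracy on items whose answer is 'nonword' = Φ(d'/2 + c)

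Start at c = 0, hold d' fixed, and move c by s toward 'word', so that c = −s.

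**Worked case: d' = 2, s = 0.2**
- Baseline, both kinds of item: Φ(1.0) = 84.1%
- 'Word' items: Φ(1.2) = 88.5%, a change of +4.4 points
- 'Nonword' items: Φ(0.8) = 78.8%, a change of −5.3 points
- False word type by time contrast: 4.4 + 5.3 = 9.7 points
- Pooled over equal numbers of both: (4.4 − 5.3)/2, about −0.5 points
- Pseudohomophones, under the same model: −5.3 in Task 1 and +4.4 in Task 2, a false between-task gap of 9.7 points

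**False contrast over a range of assumptions (points)**

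| d' | s = 0.1 | s = 0.2 | s = 0.3 |
|---|---|---|---|
| 1.0 | 7.0 | 14.0 | 20.9 |
| 1.5 | 6.0 | 12.0 | 17.9 |
| 2.0 | 4.8 | 9.7 | 14.5 |
| 3.0 | 2.6 | 5.2 | 7.9 |

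**Exception versus regular words.** Both take the same answer in both tasks, so a shift moves them together. At equal baseline accuracy the false contrast is zero. If one type starts at Φ(1.0) = 84.1% and the other at Φ(1.5) = 93.3%, a 0.2 shift adds 4.4 and 2.2 points, leaving 2.2 points. This contrast is largely, not wholly, protected.

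**Simulation.** 1,500 runs per setting, two-sided 0.05, d' = 2, 20 items per word type, no change in discrimination. Assumed between-person SDs: 0.5 for d', 0.3 for baseline criterion, 0.15 for the shift. The test was a paired word-versus-nonword contrast, not the plan's full ANOVA. With n = 30, the raw-accuracy contrast was significant in 4% of runs at shift 0, 47% at 0.1, 97% at 0.2 and 100% at 0.3. With n = 60 it was 76% at 0.1 and 100% at 0.2. A test on log-linear-corrected d' stayed at about 4–6%. At n = 30 and shift 0.2 it was 3.6%, and the criterion score detected the shift in 94%. These d' scores pooled the word types on each side; scores for separate pairs use fewer items and will be noisier.

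**Key mapping.** With g and h counterbalanced across participants, n = 30 and a lean of 0.2, a motor lean toward one key gave a false raw-accuracy contrast in 2% of runs. A lean toward the answer 'word' still gave one in 95%.

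**The case against.** The case on the other side has several parts.

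- **The data allow separation.** A reader might infer that this design cannot distinguish reading from bias. The documents do not support that. Both reading tasks contain words and nonwords, so hits and false alarms are recorded. The planned breakdown would even show the tell-tale pattern of opposite movements with almost no pooled change. This stands: the gap is in the planned measure and how it is interpreted.
- **Shared drift is another problem.** A reader might blame fatigue in the last block. Lidocaine always comes last, so drift over the session would affect response time and d' as well; that is the fixed-order problem. The gating interaction includes group, so drift common to both groups would cancel if a no-lidocaine group existed. The Treatment section gives lidocaine to every participant, so no such group is evident. A bias change specific to lidocaine would not cancel in either case.
- **The fixed keys are secondary.** A reader might take the single g/h mapping as the main fault. A constant finger difference cancels when the same word type and task are compared across conditions, and counterbalancing leaves a lean toward 'word' in place.
- **Replacing accuracy with pooled d' would cost something.** It would remove the planned exception-versus-regular contrast. This stands, and the fix avoids it.
- **The size is assumed.** Nothing in the documents shows that lidocaine changes response bias, and the earlier effects the protocol reports are faster response times, which this argument does not address. This stands.

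**Conclusion.** The point holds as a gap in the prespecified analysis. As planned, a word-versus-nonword accuracy interaction with time could reflect discrimination, response bias or both, and no planned score says which. Under assumed d' = 2 and a 0.2 SD shift the false contrast is about 9.7 points, with 2.6 to 17.9 for d' of 1.5 to 3 and shifts of 0.1 to 0.3. These figures rest on the equal-variance model and a neutral starting criterion. The pseudohomophone part also rests on the inferred Task 2 answer key.

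The documents do not support the stronger conclusions that the accuracy results will be uninterpretable, that lidocaine is likely to shift bias, or that response-time effects of the perturbation are compromised. The exception-versus-regular contrast is largely safe. The change is worth making because it is cheap and protects half of the primary endpoint from a plausible misreading.

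**What to change.** Keep accuracy per word type as planned, and add the following to the Statistical Analysis section:

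1. State the correct answer for each word type in each task, and the number of items per type.
2. Prespecify d' and criterion per participant, task and condition, from the trials already recorded. Keep exception and regular words separate. In Task 1, set each against pseudohomophones and against nonwords. In Task 2, set exception words, regular words and pseudohomophones each against nonwords. Use a log-linear correction for scores near ceiling.
3. State the reading rule: attribute a word-versus-nonword accuracy interaction to reading only if d' changes as well. If only the criterion moves, report a change in response bias.

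The cost is a little more analysis, a small-count correction, and noisier scores from separate pairs than from pooled words. No extra data are needed.

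Counterbalancing the g/h mapping is optional. It deals only with a motor lean toward one key, and it may reduce comparability with the earlier typical-reader study if that used a single mapping. None of these changes removes the separate confounding from lidocaine always being last.
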